3 STUDY OBJECTIVES

3.1 Primary objective

The primary objective is to demonstrate the clinical efficacy of bimekizumab administered sc Q4W for 16 weeks compared with placebo in the treatment of TNF α -IR subjects with active PsA, as assessed by the ACR50 response.

3.2 Secondary objectives

The secondary objectives of the study are as follows:

- To assess the efficacy of bimekizumab compared with placebo
- To assess the safety and tolerability of bimekizumab
- To assess the impact of bimekizumab on patient-reported quality of life
- To assess the impact of bimekizumab on skin PSO in the subgroup of affected subjects at Baseline
- To assess the impact of bimekizumab on functional improvement

3.3 Other objectives

Other objectives are as follows:

- To assess the immunogenicity of bimekizumab
- To assess the impact of bimekizumab on extra-articular disease manifestations (dactylitis, enthesitis)
- To assess nail PSO in the subgroup of affected subjects at Baseline
- To explore the exposure-response relationship of bimekizumab
- To assess the impact of bimekizumab treatment on axial disease
- To assess the effect of bimekizumab on gene and protein expression, and explore the relationship between genomic, genetic, and proteomic biomarkers and disease biology, drug treatment and inflammatory and immune responses (from consenting subjects who agree to participate in the biomarkers substudy)
- To assess the impact of bimekizumab on social life and work productivity

4 STUDY VARIABLES

4.1 Efficacy variables

4.1.1 Primary efficacy variable

The primary efficacy variable for this study is the ACR50 response at Week 16.

4.2 Secondary variables

4.2.1 Secondary efficacy variables

The secondary efficacy variables for this study are as follows:

- Change from Baseline in Health Assessment Questionnaire—Disability Index (HAQ-DI) at Week 16
- PASI90 response at Week 4 and Week 16 in the subgroup of subjects with PSO involving at least 3% BSA at Baseline
- Change from Baseline in the Short-Form 36-item Health Survey (SF-36) Physical Component Summary (PCS) score at Week 16
- Minimal Disease Activity (MDA) response at Week 16
- ACR20 response at Week 16
- ACR70 response at Week 16
- Proportion of subjects with an Investigator Global Assessment (IGA) score of 0 (clear) or 1 (almost clear) AND at least a 2-grade reduction from Baseline at Week 4 and Week 16 in the subset of subjects with psoriatic skin lesions at Baseline
- Change from Baseline in the Patient's Assessment of Arthritis Pain (PtAAP) at Week 16
- Change from Baseline in Psoriatic Arthritis Impact of Disease-12 (PsAID-12) total score at Week 16

4.2.2 Secondary safety variables

Secondary safety variables to be assessed are as follows:

- Incidence of TEAEs
- Incidence of treatment-emergent SAEs
- Treatment-emergent adverse events leading to withdrawal from IMP

4.3 Other variables

4.3.1 Other efficacy variables

Other efficacy variables will be assessed as specified in [Table 5-1](#) (all time points not specified in [Section 4.1.1](#) or [Section 4.2.1](#) are exploratory):

- Time to ACR20, ACR50, and ACR70 response from Baseline (Day 1)
- ACR20, ACR50, and ACR70 response

- PASI75, PASI90 and PASI100 response in the subgroup of subjects with PSO involving at least 3% BSA at Baseline
- Composite endpoint composed of ACR50 and PASI90 response in subjects with PSO involving at least 3% BSA at Baseline
- Composite endpoint composed of ACR50 and PASI100 response in subjects with PSO involving at least 3% BSA at Baseline
- Proportion of Psoriatic Arthritis Response Criteria (PsARC) responders
- Psoriatic Arthritis Disease Activity Score (PASDAS) categories
- Change from Baseline in the PASDAS
- MDA response
- Very Low Disease Activity (VLDA) response
- Proportion of subjects with an IGA score of 0 (clear) or 1 (almost clear) AND at least a 2-grade reduction from Baseline in the subset of subjects with psoriatic skin lesions at Baseline
- Disease Activity Index for Psoriatic Arthritis (DAPSA) score categories
- Change from Baseline in DAPSA score
- Change from Baseline in the Disease Activity Score-28 based on C-reactive protein (DAS28[CRP])
- Change from Baseline in all individual ACR core components:
 - SJC
 - TJC
 - HAQ-DI
 - PtAAP
 - Physician's Global Assessment of Psoriatic Arthritis (PhGA-PsA)
 - Patient's Global Assessment of Psoriatic Arthritis (PGA-PsA)
 - High sensitivity C-reactive protein (hs-CRP)
- Enthesitis-free state based on the Leeds Enthesitis Index (LEI) in the subgroup of subjects with enthesitis at Baseline
- Change from Baseline in the LEI in the subgroup of subjects with enthesitis at Baseline
- Enthesitis-free state based on the Spondyloarthritis Research Consortium of Canada (SPARCC) index in the subgroup of subjects with enthesitis at Baseline
- Change from Baseline in SPARCC index in the subgroup of subjects with enthesitis at Baseline
- Dactylitis-free state based on the Leeds Dactylitis Index (LDI) in the subgroup of subjects with dactylitis at Baseline

- Change from Baseline in the LDI in the subgroup of subjects with dactylitis at Baseline
- Proportion of subjects with a decrease of HAQ-DI from Baseline of at least 0.35 in those subjects with HAQ-DI > 0.35 at Baseline
- Change from Baseline in the Bath Ankylosing Spondylitis Disease Activity Index (BASDAI) in the subgroup of subjects with axial involvement defined by a score of ≥ 4 at Baseline
- Change from Baseline in the modified Nail Psoriasis Severity Index (mNAPSI) score in the subgroup of subjects with psoriatic nail disease at Baseline
- Change from Baseline in PsAID-12 total score
- Change from Baseline in the individual domain scores of PsAID-12
- Proportion of subjects achieving PsAID-12 total score ≤ 4
- Proportion of PsAID-12 responders (decrease from Baseline in PsAID-12 total score ≥ 3) in subjects with PsAID-12 total score > 3 at Baseline
- Change from Baseline in the Psoriatic Arthritis Quality of Life (PsAQoL) total score
- Change from Baseline in the SF-36 PCS and SF-36 Mental Component Summary (MCS) scores, as well as the 8 domain scores (Physical Functioning, Role Physical, Bodily Pain, General Health, Vitality, Social Functioning, Role Emotional, and Mental Health)
- Change from Baseline in Functional Assessment of Chronic Illness Therapy (FACIT)-Fatigue subscale score
- Proportion of FACIT-Fatigue subscale responders (subjects with a minimum clinically-important difference for FACIT-Fatigue subscale score, defined as an increase of ≥ 4) in subjects with FACIT-Fatigue subscale score ≤ 48 at Baseline
- Change from Baseline in Work Productivity and Activity Impairment Questionnaire-Specific Health Problem (WPAI-SHP) v2.0 adapted to PsA scores
- Responses to the EuroQol-5D-3-Level (EQ-5D-3L) dimensions
- Change from Baseline in EQ-5D-3L Visual Analog Scale (VAS) scores
- Change from Baseline in Physician's Global Assessment of Arthritis (PhGA-Arthritis)
- Change from Baseline in Patient's Global Assessment of Arthritis (PGA-Arthritis)

4.3.2 Other safety variables

Other safety variables to be assessed are:

- Change from Baseline in vital signs (blood pressure [BP], temperature, and pulse rate)
- Standard 12-lead electrocardiogram (ECG) results
- Change from Baseline in clinical laboratory values (hematology, biochemistry and urinalysis)
- Change from Baseline in Patient Health Questionnaire-9 (PHQ-9)

Physical examination findings considered clinically significant changes since the physical examination at the Screening Visit will be recorded as AEs.

4.3.3 Pharmacokinetic variable

The PK variable is the plasma concentration of bimekizumab.

4.3.4 Pharmacogenomic variables

Additional blood samples will be collected from subjects who consent to participate in the substudy at specific time points and stored at -80°C for up to 20 years.

Genomic, genetic, epigenetic, proteins, and metabolite biomarkers may be measured to evaluate the relationship with response to treatment with bimekizumab, psoriatic arthritis disease biology, and inflammatory and immune response processes. The nature and format of these tentative substudy analyses will be determined when the results of the main study are made available.

The candidate exploratory variables are the blood or blood derivative (eg, serum) concentrations of cytokines and chemokines of relevance to IL-17A/F signaling pathway and psoriatic arthritis biology. Additional variables may include but will not be limited to serum complement concentrations.

4.3.5 Immunological variables

The immunological variables are the anti-bimekizumab antibody status and the treatment-emergent antibody positivity derived from anti-drug antibody assays.

5 STUDY DESIGN

5.1 Study description

This is a Phase 3, multicenter, randomized, double-blind, placebo-controlled study to evaluate the efficacy and safety of bimekizumab in subjects with active PsA. To be eligible to participate in this study, subjects must be adults with a diagnosis of active PsA based on the CASPAR criteria, and have disease with TJC ≥ 3 and SJC ≥ 3 , as well as an inadequate response (lack of efficacy after at least 3 months of therapy at an approved dose) or intolerance to treatment with 1 or 2 TNF α inhibitors for either PsA or PSO. Detailed inclusion and exclusion criteria are presented in [Section 6.1](#) and [Section 6.2](#), respectively.

The study will include 3 periods: a Screening Period (≥ 14 days to ≤ 35 days), a Double-Blind Treatment Period (16 weeks), and a Safety Follow-Up Period (20 weeks after the final dose of IMP). The maximum study duration per subject will be up to 37 weeks.

Eligible subjects will be randomized 2:1 to receive 1 of 2 blinded treatments (bimekizumab 160mg sc Q4W or placebo) and will remain on their allowable background medication. Details of the Treatment Period are provided in [Section 5.3](#).

Subjects completing Week 16 and meeting eligibility criteria are eligible for enrollment in an OLE study to continue to receive bimekizumab.

A final analysis of all available data will be undertaken after all randomized subjects have completed 16 weeks of treatment or have been withdrawn from the study. The purpose of this analysis is to compare the efficacy and safety of the 2 treatment arms. For subjects who are

ineligible for the OLE study at Week 16, a follow up analysis will be undertaken after the SFU Visit.

Additional details for data monitoring in this study are provided in [Section 14.8.1](#). A detailed schedule of study assessments is presented in [Table 5-1](#) and a study schematic diagram is presented in [Figure 5-1](#).

5.2 Screening Period/Baseline

The Screening Period will last for a minimum duration of 14 days and a maximum duration of 35 days and will involve obtaining laboratory data and verifying that the doses of nonsteroidal anti-inflammatory drugs (NSAIDs) or permitted DMARDs, if used to treat PsA, are stable. The Screening Period will also enable washout of any medications not permitted for use during the study.

5.2.1 Within-study rescreening/retesting requirements

Rules for rescreening or repetition of screening tests within the study are listed below:

- Subjects who fail to meet the eligibility criteria for PHQ-9, electronic Columbia-Suicide Severity Rating Scale (eC-SSRS), or the tuberculosis (TB) questionnaire **are not allowed** to be rescreened.

The Medical Monitor must be contacted for confirmation of rescreening/retesting in all other cases.

- Subjects who initially fail to meet selected eligibility criteria (eg, documented completion of latent tuberculosis infection [LTBI] prophylactic therapy) may be rescreened.
- Subjects for whom eligibility assessments could not be completed as planned (eg, for technical reasons) within the defined Screening Period of 35 days may be rescreened.
- Subjects with individual laboratory screening tests for which the results are exclusionary, can be retested.

Of note, repetition of laboratory screening tests within the Screening Period is permitted for technical reasons (eg, frozen sample, expired laboratory kit) without contacting the Medical Monitor.

5.3 Treatment Period

5.3.1 Double-Blind Treatment Period

During the Double-Blind Treatment Period, subjects will be randomized 2:1 (stratified by region and prior TNF α inhibitor exposure [inadequate response to 1 or 2 prior TNF α inhibitors, or intolerance to TNF α inhibitors]) to receive 1 of 2 blinded treatment regimens.

Investigational medicinal product treatment details are provided in [Section 7.2](#).

Visit windows of ± 3 days are allowed from the first dose at all visits through Week 16. The visit window is relative to the Day 1 (Baseline) Visit.

Bimekizumab and placebo will be administered sc by unblinded study personnel at the clinical site.

The time between IMP doses should be ≥ 21 days and ≤ 35 days during the Double-Blind Treatment Period. The Double-Blind Treatment Period is 16 weeks in duration.

Subjects discontinuing IMP during the Double-Blind Treatment Period will return for all scheduled visits through Week 16 and the SFU Visit (20 weeks after the final dose of IMP) as applicable ([Section 8.4](#)). Subjects withdrawing from the study will have an Early Termination (ET) Visit and a SFU Visit 20 weeks after the final dose of IMP, as applicable.

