14 STATISTICS

A description of statistical methods follows and will be described in more detail in the SAP.

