The statistical hypothesis for the ACR50 response at Week 16 is that the conditional odds ratio for ACR50 response in the bimekizumab treatment compared with placebo is equal to 1.

A logistic regression model will be used to assess the treatment effect on ACR50 response at Week 16. The model will include fixed effects for treatment. The suitability of including the randomization stratification variables, prior TNF α exposure and region will be assessed, and will be added to the model if appropriate. Comparisons will be made using the 2-sided Wald test at a significance level of $\alpha=0.05$ (ie, H₁ [Figure 14-1](#)). The odds ratio vs placebo, p-value and the 95% CI will be calculated.

Any use of prohibited or rescue medications through Week 16 would constitute an important protocol deviation which would be accounted for when the sensitivity analysis based on the PPS is performed (see Section [14.3.1.1.1](#)).

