Any missing data at Week 16 that is not preceded by an intercurrent event (ie, discontinuation of study medication) will also be imputed based on a predefined MI model. In MI, the missing value is replaced by a set of plausible values, where each value is a Bayesian draw from the conditional distribution of the missing data given the observed data. Intermittent missing data

will be imputed using the MCMC method, followed by monotone regression for monotone missing data.

The statistical model for continuous endpoints for the comparison of bimekizumab and placebo will be an ANCOVA model with treatment, prior TNF α exposure and region as fixed effects and the Baseline value as covariate. The statistical hypothesis for the continuous variables at Week 16 is that the treatment difference between the bimekizumab treatment group and placebo is equal to 0.

All secondary efficacy variables will also be summarized based on observed case data as well as multiple imputation using the modified composite estimand for binary variables.

Variables that are included in the hierarchy will additionally be rerun using the COVID-free Set.

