Other binary and continuous efficacy variables will also be summarized based on observed case (OC) data (ie, subjects with missing data or who have prematurely discontinued study treatment are treated as missing). Further, binary outcomes will be summarized using the modified composite estimand.

The time to ACR20/50/70 response will be estimated and presented using the Kaplan Meier product limit method for each treatment. Time to a given response will be defined as the time in days from Baseline until the first date when the response is achieved. Subjects who discontinue study treatment prior to achieving a response will be censored at the date of study treatment discontinuation. The median time to response, including the 2-sided 95% CI, will be calculated for each treatment. Between group differences will be analyzed using a log-rank statistic.

The time to ACR20/50/70 endpoints will be analyzed using OC data. All other efficacy variables will be analyzed based on imputed and on OC data.

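### The log-rank test for time to ACR20/50/70 names no strata although randomization is stratified; stratifying it is a free, minor improvement

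*Protocol*

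**What the plan says.** Protocol Section 5.3.1: "subjects will be randomized 2:1 (stratified by region and prior TNF"-alpha inhibitor exposure). The second factor distinguishes inadequate response to one or two inhibitors from intolerance.

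Protocol Section 14.3.2, on time to ACR20/50/70, fixes Kaplan-Meier estimation, the time origin and the median with its 95% CI. On censoring it says: "Subjects who discontinue study treatment prior to achieving a response will be censored at the date of study treatment discontinuation". On the data: "The time to ACR20/50/70 endpoints will be analyzed using OC data". On the test: "Between group differences will be analyzed using a log-rank statistic". It names no stratification factors.

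Elsewhere the factors are named. The ANCOVA for the secondary continuous endpoints (Section 14.3.1.2) has prior TNF-alpha "exposure and region as fixed effects and the Baseline value as covariate". The supportive ANCOVA of the ACR components (Section 14.3.1.1.1, item 3) has the same terms. The primary logistic model (Section 14.3.1.1) treats them conditionally: "The suitability of including the randomization stratification variables" is to be assessed first.

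Section 4.3.1 lists time to response among the other efficacy variables. It is not among the variables that Section 14.3.1.2 lists for the testing hierarchy, and Section 14.9 gives it no power statement.

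**The concern.** Stratified randomization balances the arms within each stratum. An unstratified log-rank test still estimates its variance as if that balance had been left to chance. If response speed differs between strata, the variance is too large for the design and the test rejects less often than 5% under the null. It also pools patients with different response speeds, which dilutes the treatment contrast. Both effects cost power.

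At stake is the precision of the onset-of-response comparison, and consistency with the analyses in the same protocol that do carry the randomization factors.

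**Working it through.** **1. The plan's own figure.** The protocol gives no power, event count or hazard ratio for time to response. The nearest figure is the 96% power for ACR50 at Week 16 (Section 14.9.1: 260 vs 130, 26% vs 10%, two-sided 0.05, chi-square with continuity correction).

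- Correction: √n′ = √n − a/(4√n), with a = 2(1 + 1/k)/d, n = 130, k = 2, d = 0.16. So a = 18.75, √n′ = 11.402 − 0.411 = 10.991 and n′ = 120.8.
- Pooled rate: (0.10 + 2 × 0.26)/3 = 0.2067.
- z = [0.16 × 10.991 − 1.96 × √(0.2067 × 0.7933 × 1.5)] / √(0.09 + 0.1924/2) = (1.7585 − 0.9720)/0.4315 = 1.823.
- Power = Φ(1.823) = 96.6%. The stated 96% reproduces.

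**2. Translation to time to ACR50.** With constant hazards, the hazard ratio is ln(1 − 0.26)/ln(1 − 0.10) = 2.86. Expected responders are 260 × 0.26 + 130 × 0.10 = 80.6.

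**3. The two tests.** At each visit with n at risk, n₁ of them on bimekizumab, and d responders, E = d·n₁/n and V = d(n₁/n)(1 − n₁/n)(n − d)/(n − 1). The statistic (Σ(O − E))²/ΣV is compared with 3.841. The unstratified test forms these sums over all subjects. The stratified test forms them within strata and then adds.

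**4. Simulation.** 390 subjects, 2:1, visits at Weeks 4, 8, 12 and 16, 2,500 trials per cell. Assumptions not in the protocol:

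- 12 strata: four regions (Section 14.3.3 names four only as examples) by three TNF categories, with shares 10/45/20/25% and 77/11/12%;
- blocks of 3 and 5% censoring;
- a between-stratum SD of the log-hazard from 0 to 1.0. One SD multiplies the hazard by e^0.3 = 1.35, e^0.6 = 1.82 or e^1.0 = 2.72.

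The overall placebo rate is held fixed and the hazard ratio is constant within strata, so the bimekizumab rate shown is exact only at SD 0.

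Power in %, unstratified / stratified:

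| Week 16 rates | HR | SD 0 | SD 0.3 | SD 0.6 | SD 1.0 |
|---|---|---|---|---|---|
| 10% vs 26% (protocol, ACR50) | 2.86 | 97.8 / 97.6 | 97.7 / 98.0 | 96.7 / 97.4 | 95.4 / 97.4 |
| 10% vs 20% (assumed) | 2.12 | 72.8 / 72.8 | 70.4 / 71.0 | 70.1 / 72.4 | 65.6 / 72.2 |
| 25% vs 38% (assumed, ACR20-like) | 1.66 | 72.8 / 72.9 | 71.2 / 71.6 | 68.2 / 72.1 | 57.3 / 72.4 |

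Rejection under the null, unstratified: 4.7 to 5.6% at SD 0 to 0.3, 3.9 to 4.4% at SD 0.6, and 2.8 to 4.1% at SD 1.0. Stratified: 4.3 to 5.6% throughout. The Monte Carlo standard error is about 0.4 points near 5% (√(0.05 × 0.95/2500)) and 0.9 points near 72%.

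**5. A second set-up.** 8,000 trials per setting, region shares 40/30/20/10%, TNF shares 15/65/20% and 2% dropout per visit gave the same pattern. With strong strata (per-visit log-odds shifts up to ±1.0 and ±0.6), power was 67% vs 75% for an ACR20-like outcome and 60% vs 62% for an ACR70-like outcome, with size 3.3% vs 4.9%. With moderate strata (up to ±0.5 and ±0.3), power was 78% vs 80% and 62% vs 62%. With strata that do not matter, stratifying cost at most 0.4 points.

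**The case against.** The strongest reply is that the unstratified reading rests on silence. A stratified log-rank is also a log-rank statistic, and Section 14 opens with: "A description of statistical methods follows and will be described in more detail in the SAP". The SAP is not at hand and may already stratify the test. This stands as a limit: a reader might infer that the sponsor has committed to an unstratified test, and the protocol does not say so. Against it, Section 14.3.2 fixes origin, censoring, data and test for this variable, and the protocol names the factors where it uses them. Unstratified is therefore the plain reading.

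A second reply is that no internal rule is broken. A reader might infer that the log-rank departs from the analysis of every continuous endpoint. It does not: Section 14.3.2 summarizes the other continuous variables by unadjusted means and the other binary variables by unadjusted proportions, and the primary logistic model takes the factors only if suitable. The contrast holds for the secondary continuous endpoints and the ACR components. But those unadjusted summaries are descriptive, and the log-rank is the only between-group test that Section 14.3.2 specifies.

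A third reply is that some strata would be nearly empty. The smallest holds about 4 of 390 subjects under the first set of shares (0.10 × 0.11 × 390) and about 6 under the second (0.10 × 0.15 × 390). That calls for a pooling rule, but the simulations already include such strata and show no material loss.

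**Conclusion.** The point holds as a minor, free improvement. As written, the test ignores the randomization factors. If those factors are prognostic, it is somewhat conservative and loses power: 0 to 2 points at the protocol's ACR50 rates, and about 2 to 4 points for the smaller assumed effects at SD 0.6. Losses of about 7 to 15 points appear only at SD 1.0 with response rates that the protocol does not give. With non-prognostic strata there is no loss.

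A reader might infer that the test is conservative in any event, or that the large losses are to be expected. The protocol gives no information on how strongly region or prior TNF-alpha exposure predicts response, so neither follows. Nor is any confirmatory result at risk: type I error is not inflated, the variable is outside the hierarchy, and the sample size does not depend on it. The sizes rest on the assumed stratum shares, censoring, block size and stratum effects listed above.

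**What to change.** In Section 14.3.2, replace the unqualified log-rank statistic with a log-rank test stratified by region and prior TNF-alpha inhibitor exposure as randomized. Add a rule for pooling sparse strata, fixed before unblinding. A stratum that contains only one arm adds nothing to either sum, so the rule serves to keep information and to rule out later choices. Kaplan-Meier curves and medians may stay unstratified. If an unstratified test is intended, the section should say so and give the reason.

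The cost is one phrase in the protocol or SAP and one option in the analysis program. It needs no new data and does not change the sample size or the testing hierarchy.
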